Caregiver smoking is an important cause of morbidity and mortality in both adult smokers and their children who are involuntarily exposed to secondhand smoke (SHSe). Our research has found that caregivers who visit the Pediatric Emergency Department (PED) with their children have a high prevalence of smoking (up to 48%), their children have high levels of SHSe equivalent to that of active smokers, and they regularly use the PED for nonurgent, SHSe-related complaints. These smokers are motivated to quit and eager to receive cessation counseling in this setting. Annually, more than 3 million PED visits involve treatment of children with SHSe-related illnesses. These visits provide a unique “teachable moment” to motivate caregiver quitting, given the relationship between quitting and improvements in their child’s health. Because of the long, unavoidable wait times and the frequent use of the PED for non-urgent care, this is an ideal venue for intervening with this population. Moreover, we and others have demonstrated the feasibility of conducting complex randomized trials in PEDs without disrupting clinical flow. Building on our prior research, we propose to conduct the first randomized trial to test whether a cessation intervention in the PED setting can reduce caregiver smoking and decrease children's SHSe. This study will test the efficacy of a cessation intervention for caregivers in a large, inner-city PED that is a major nodal site for the federally funded Pediatric Emergency Care Applied Research Network (PECARN). The proposed Screening, Brief Intervention, and Assisted Referral to Treatment (SBIRT) will highlight the effects of SHSe on their child’s health. We will randomize 750 caregivers who smoke who present to our PED with their child who has a SHSe-related illness to either one of two conditions: 1) SBIRT; or 2) Healthy Habits Control (HHC). The SBIRT condition will use components shown to be effective in the out-patient setting but not yet tested in the PED setting. It will include a brief form of the Clinical Practice Guideline: Treating Tobacco Use and Dependence, motivational interviewing, engaging and personalized materials on the effects of smoking and SHSe, immediate access to caregivers’ choice of cessation resources (e.g., Quitline, smokefree.gov, or smokefreeTXT), a 12-week supply of nicotine replacement therapy and booster materials for 12 weeks. The HHC program has been previously developed and used in the out-patient setting, and will be used as an attention control in which caregivers will receive instruction on healthy lifestyle choices to improve their child’s health. Cessation assistance will be offered at the study’s conclusion. If effective, the SBIRT model could be routinely used in the PED setting, which could reach at least one million smokers a year, and could result in significant reductions in caregivers' tobacco use, SHSe-related pediatric illness, and costs in this population. In addition, our results will inform the conduct of public health research efforts aimed at adults via the PED. If successful, we will create a comprehensive package of materials for disseminating the implementation of the intervention throughout PECARN and non-PECARN PEDs, and EDs nationwide. This study will also assess the prevalence and correlates of cannabis smoke exposure (CSE) among PED patients who are in the SHS-exposed group.

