
PURPOSE

We propose to conduct the first randomized controlled trial to test whether a cessation intervention in the PED setting can reduce caregiver smoking and decrease children's SHSe.

Primary Aim 1: To evaluate the efficacy of the SBIRT compared to Healthy Habits Control (HHC) condition. Primary outcomes are self-reported prolonged abstinence and point prevalence at 6-weeks and 6-months post-enrollment, validated in all participants via expired carbon monoxide and salivary cotinine. Secondary outcomes include number of cigarettes smoked, quit attempts, readiness to quit, and use of cessation resources.

Hypothesis 1: Caregivers who receive the SBIRT will have higher prolonged abstinence and point prevalence cessation rates compared to caregivers in the HHC condition.

Primary Aim 2: To evaluate the efficacy of the SBIRT on reducing children's SHSe. Outcomes are caregiver reports of total home/car smoking bans and reductions in SHSe (validated using salivary cotinine in children).

Hypothesis 2: Children of SBIRT caregivers will have higher total home/car smoking bans and lower home/car smoking exposure compared to children of HHC caregivers.

Primary Aim 3: To explore mediators and moderators of the SBIRT outcomes.

Hypothesis 3: The SBIRT intervention effect on prolonged abstinence and point prevalence cessation rates will be mediated by the caregiver's perception of the risk of smoking on their child's health and the caregiver's motivation to quit over time. The intervention effect will be moderated and attenuated by factors such as household smokers, financial strain, and low social support to quit.

Secondary Aim 1: To conduct a cost analysis to determine the numbers of SHSe-related PED visits and hospitalizations in children of caregivers in the SBIRT condition compared to children of caregivers in the HHC condition. This will provide a basis for a future, full-scale cost-benefit analysis.

Secondary Aim 2: Using the findings from this project and our prior research, we will develop a manual of operations and a comprehensive package of provider and patient materials that will be disseminated for use in other PEDs and EDs nationwide.

Secondary Aim 3: To quantify the prevalence and identify correlates of Cannabis Smoke Exposure and SHSe among SHS-exposed PED patients.

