During the approximately 48-month or longer study enrollment period, CRCs and approximately 1-2 pairs of clinical counselors/intake coordinators/research coordinators (i.e., one from each condition) will provide study coverage every weekday. This increases the opportunities for recruitment and delivery of the interventions. Our prior research demonstrates that approximately 3 CRCs will be more than adequate to recruit 750 caregivers. Enrollment times will represent peak PED volumes. CRCs will screen consecutive caregivers of patients presenting to the PED using CCHMC's EMR system, Epic. CRCs will identify caregivers by reviewing Epic records of registered patients. A secure database will be used which will include all patients, their age, gender, race, chief complaint, enrollment status, and reasons for non-enrollment.

Eligible caregiver adult participants must: 1) be > or equal to age 18; 2) be accompanying a child 0-17 years of age 2) be a daily smoker; 3) speak and read English (if shown to be efficacious, we will translate the intervention materials and test it with multi-lingual CRCs and clinical counselors/intake coordinators/research coordinators in a future trial), 4) have a permanent address and a working cell or landline number, 5) live within an approximately 50 mile radius of CCHMC (since we will conduct home visits.)

Eligible child participants must: 1) Not be a current smoker of tobacco or marijuana; 2) present to the PED with : (a) a stable condition, that is, patients who are not critically ill and do not require immediate treatment and intervention by the PED practitioner (triage levels 2-5) and (b) a potentially SHSe-related complaint (which will include complaints such as wheezing, difficulty breathing, cough, ear infection, cold, ear pain, runny nose, congestion, flu, asthma, shortness of breath) as outlined by the U.S. Surgeon General;⁴⁸ or SHSe-related discharge diagnosis.

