If both caregivers are present and eligible, they will be asked to identify the primary caregiver and if one or both want to receive the intervention. Although both caregivers may receive the intervention, only the primary caregiver will be enrolled and assessed for data collection. Based on our previous studies, we know that both caregivers are present in the PED and eligible for the study less than 5% of the time. Child participants will be excluded if they have a tracheostomy. Adult caregivers will be excluded if they are tobacco chewers only, using pharmacologic cessation treatment, plan to move within the study period (if they do not know their new address), or do not have a working phone number or permanent address. The CRC will obtain informed consent.

For the CSE study aim, caregiver survey data on cannabis use and child CSE and stored child urine samples will be assessed from the child-parent participants in the SHS-exposed group who consented to providing this additional data and child urine samples. Eligibility criteria for the CSE study aim of this project are the same as the SHS-exposed group, and with the additional eligibility criteria that they will have: caregiver survey data on cannabis use and child CSE; a sub-sample of children have stored urine samples available for lab analysis of biomarkers of exposure; and provided informed consent to analyze the associated data and child urine samples.

POTENTIAL BENEFITS

There may be no direct benefit to adult participants other than the counseling and NRT that they will receive from the study in the intervention condition. The intervention may help them decrease their smoking. Cessation would reduce their risk of contracting lung and/or oral cancer, chronic obstructive pulmonary disease, coronary heart disease, or periodontal disease. Intervention participants will become more aware of the health risks

associated with smoking cigarettes than they may have had prior to their participation in this study. Even if they do not make a quit attempt, they will have been given information on how to go about quitting that could be useful to them in the future.

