a follow-up salivary cotinine level on children to validate total home smoking bans, and (3) complete assessment of outcomes. Cotinine is generally accepted to be the best of the available biomarkers, with over 95% specificity and sensitivity, it is noninvasive, and easily obtained in young children.^{85,86} [ENREF 114](#) A standard protocol will be used to collect saliva samples from each child at baseline, 6-weeks, and possibly 6 months. Cotinine analyses will be performed with Enzyme Immunoassay techniques by Salimetrics LLC, State College, PA. In the child samples, the lower limit of cotinine sensitivity is 0.05 ng/ml (range of sensitivity: 0.06-200 ng/ml); undetectable cotinine values will be recorded as 0 ng/ml.^{87,88} Alternatively, if additional funds are available, cotinine analyses may be assessed with liquid chromatography mass spectrometry (LCMS). Caregiver abstinence will be established if the caregiver's expired carbon monoxide level is at or below 6 ppm; salivary cotinine may be assessed to confirm abstinence in caregivers who report they have quit if their exhaled carbon monoxide does not provide verification. At 6 months, we will assess all caregivers via phone or email, and validate self-reported abstinence and total home smoking bans via expired carbon monoxide testing and/or salivary cotinine.

Data Management

Data management will occur at CCHMC. Participants will complete the baseline assessment on a web-enabled tablet research computer. Data will be collected and managed using REDCap (Research Electronic Data Capture).⁹² [ENREF 116](#) The Redcap Mobile App may also be used in order to scan barcodes on samples.

DATA ANALYSIS

Sample Size and Power Estimates

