Primary Aim 2, Hypothesis 2: We will evaluate the effectiveness of the SBIRT on total home/car smoking bans and on child SHSe which will be measured by both caregiver report and child salivary cotinine, as recommended by Halterman et al.⁸⁷ The reliability of caregiver's reports will be examined by comparing amount of smoking and SHSe levels reported at 6-months using Pearson's correlations. For validation, we will compare the child's salivary cotinine concentrations for those reporting total home/car smoking bans and those not, we shall also examine the change in cotinine levels from baseline for those initiating bans versus not. The computational procedure will use data from the 2 measurement points, controlling for the within-subject correlation of measures repeated over time.^{97,98} The main analysis will use GLMM, first to assess the intervention effect alone and then including covariates. First, we will investigate immediate intervention effects based on change from baseline to 6-weeks post-intervention. Next, we will investigate change from 6-weeks to 6-months to examine maintenance effects. To examine overall change, we will use GEE, examining linear and quadratic terms for time, group, and group \times time interactions as explanatory variables.⁵² Use of NRT, described above, may be of particular interest as a covariate for this analysis.

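### The child criterion bars smokers only, so a child up to 17 who vapes or uses other nicotine is eligible and that child's cotinine is read as secondhand smoke exposure

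*Combined protocol and SAP*

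**What the plan says.** Under Participant Screening, Enrollment, and Exclusion, the caregiver must "be accompanying a child 0-17 years of age". The first child criterion is "Eligible child participants must: 1) Not be a current smoker of tobacco or marijuana". The one listed child exclusion is "Child participants will be excluded if they have a tracheostomy". Neither mentions vaping, smokeless tobacco or other nicotine.

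For adults the same section does separate smoking from another form of tobacco use: "Adult caregivers will be excluded if they are tobacco chewers only".

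Child cotinine has three uses:

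- Primary Aim 2 lists as an outcome "reductions in SHSe (validated using salivary cotinine in children"), and its analysis evaluates "total home/car smoking bans and on child SHSe which will be measured by both caregiver report and child salivary cotinine".
- The analysis text for Primary Aim 1 compares child cotinine between arms by t-test, analysis of covariance and a repeated-measures model.
- The analysis text for Primary Aim 2 compares cotinine between children with and without a reported ban, and examines its change from baseline when a ban starts.

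The Biochemical Validation section supports this choice: "Cotinine is generally accepted to be the best of the available biomarkers". It gives assay limits for child samples but no rule for a child's own intake. Item 7 of the baseline measures (Child's SHSe) asks about other people who smoke around the child. Table 1 lists nothing on the child's own use at any time point.

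**The concern.** Cotinine is a metabolite of nicotine. It shows how much nicotine reached the child, not where it came from. If the child vapes or chews, the assay result is still entered as exposure to other people's smoke.

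The criterion already removes children who smoke, so the plan accepts that some own use disqualifies a child. The wording stops at smoking, although the range runs to 17 and the adult criteria recognise tobacco use without smoking. The criterion is also stated for enrolment only, whereas saliva is taken at baseline, at 6 weeks and possibly at 6 months. A child could start using nicotine in between.

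At stake are the cotinine comparisons in Aim 2 and the comparison that supports reported bans. Own users add variation that has nothing to do with the caregiver's smoking or the household's rules, and the intervention may not move their values.

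**Working it through.** **Text check.** Set side by side, the criterion covers smoking only, the exclusion covers tracheostomy only, the SHSe questions cover other people only, and the analysis sections contain no exclusion or sensitivity analysis for own use. The gap is in the protocol text. Appendices E, G and H (eligibility screener, 6-week and 6-month assessments) appear by title only, so their items cannot be checked.

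**No plan figure to reproduce.** The documents give no mean, standard deviation or power for child cotinine. The power stated for Aim 2 concerns smoking bans (a difference of 12% with 300 per group, 11% with 375) and does not involve cotinine.

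**Illustration of scale. Every input is an assumption.** Let p be the share of all children who use nicotine without smoking, R the ratio of their cotinine to that of exposure-only children, and 1.2 the standard deviation of log cotinine (variance 1.44).

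- Variance inflation: V = 1 + p(1 − p)(ln R)² / 1.44
- Effective share of the sample: 1 / V
- Power of a comparison that would have 80% without own users, noise only: Φ(2.80/√V − 1.96)
- The same, if the intervention does not change own users' cotinine (dilution): Φ(2.80(1 − p)/√V − 1.96)

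Worked case, p = 3% and R = 30: 0.03 × 0.97 × 3.401² = 0.337; V = 1 + 0.337/1.44 = 1.234; 1/V = 0.81; noise-only power = Φ(2.80/1.111 − 1.96) = Φ(0.56) = 71%.

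| p | R | V | 1/V | Power, noise only | Power, with dilution |
|---|---|---|---|---|---|
| 3% | 3 | 1.024 | 0.98 | 79% | 77% |
| 1% | 10 | 1.036 | 0.96 | 79% | 78% |
| 5% | 10 | 1.175 | 0.85 | 73% | 69% |
| 3% | 30 | 1.234 | 0.81 | 71% | 69% |
| 5% | 30 | 1.382 | 0.72 | 66% | 62% |

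With wider assumptions (p from 0.5% to 5%, R from 20 to 100, standard deviation 1.0 to 1.5) and dilution included, the range is 79% down to 47%. A range this wide shows that the inputs decide the answer.

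**Plausibility of p.** It is a share of all children aged 0-17. If 20% were adolescents (an assumption), p = 5% would mean 5/20, or one adolescent in four, using nicotine without smoking; p = 1% would mean 1/20, or one in twenty. The lower rows are easier to defend.

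**The case against.** **Bias between arms.** A reader might infer that the treatment comparison is biased. The documents do not support that: allocation is random, so own use at entry should balance on average.

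**A large loss of power for the trial.** A reader might take 66% or 71% as the trial's power. Those figures rest on assumed inputs, and the plan claims no power for cotinine. Nor can they be tied to the 300 per group in the Sample Size section, which counts caregivers retained at 6 months. The Study Design Overview calls for child saliva at 6 months only where the caregiver reports abstinence and bans, so the 6-month cotinine sample is a subset.

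**Truthful ban reports overturned.** The plan contains no such step. It compares cotinine between ban groups and applies no individual threshold that cancels a report. Steady own use also partly cancels in change from baseline, and log transformation limits the pull of extreme values.

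**Own users can never be found afterwards.** The opening summary says of exposed children that "their children have high levels of SHSe equivalent to that of active smokers". That suggests a cotinine cut-off alone is unreliable. The argument cannot, however, be joined to a 30-fold ratio: ln 30 / 1.2 = 2.8 standard deviations, so many such values would stand out, and the Preliminary Analyses already look for out-of-range values. If levels overlap instead, R is small and so is the added variance, as the 3-fold row shows.

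**The question may already be asked.** The instruments could contain it, and the purpose of the criterion is inferred rather than stated. Both are fair. What stands is that the protocol text requires no such question and the analysis plan makes no use of an answer.

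**Conclusion.** The point holds as a gap in a stated rule. Under the protocol text a child up to 17 who uses nicotine without smoking is eligible, and that child's cotinine enters the Aim 2 cotinine comparisons and the ban-validation comparison as secondhand exposure. The consequence is added noise, dilution and misattributed exposure in adolescents.

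The size is unknown. It depends on the share of adolescents, the share of own users among them, and how far their cotinine exceeds that of exposed children; the documents give none of these. Under the assumptions shown it runs from negligible to material. Caregiver abstinence and reported bans do not depend on child cotinine and are unaffected. The change is worth making because it is specific and cheap, not because a large loss has been shown.

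**What to change.** 1. Reword the child criterion to: *not a current user of any tobacco, nicotine (including e-cigarettes) or marijuana product*.
2. Record the child's own use at baseline, before allocation is known, and again at each later saliva collection. Ask older children privately; the existing assent age (over 10) is a natural threshold.
3. Exclude children with own use at baseline from the cotinine analyses. Their caregivers, once randomised, stay in the abstinence and ban analyses.
4. Otherwise keep the main cotinine comparison as randomised. Own use reported at follow-up arises after randomisation and could be influenced by a caregiver cessation programme, so dropping those samples from the main analysis could itself introduce bias.
5. Pre-specify two sensitivity analyses of the cotinine and ban-validation comparisons: one excluding samples with own use reported at follow-up, and one limited to children aged 10 or younger. The second needs only age, so it also covers children enrolled before the question was added.

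The cost is one extra item, with privacy arrangements for older children; a few adolescents excluded, with their caregivers where this happens at screening; and lower precision in the age-restricted analysis, which drops everyone aged 11 to 17.

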
Given our prior experience⁵⁴ and proposed techniques, we conservatively project an 80% retention rate at 6 months.

Outcome Measures. Primary outcomes will be caregiver prolonged abstinence and 7-day point prevalence of tobacco use at 6-weeks and 6-months. Secondary caregiver outcomes will include cigarettes smoked, quit attempts, readiness to quit, and use of NRT and cessation resources (QL, smokefreeTXT, smokefree.gov). Child outcomes will be presence or absence of total home/car smoking bans, reported SHSe, and number of SHSe-related PED visits and hospitalizations at CCHMC.

Baseline Assessment. (Table 1) The brief baseline assessment (T0) will be conducted using a self-administered electronic survey to be completed on a tablet computer. The assessment items chosen are empirically validated measures from studies conducted with low-income disadvantaged study populations.^{42,66-71,39,63-68} The items are brief, easily comprehensible, and take into account low literacy levels. They are as follows:

Table 1: Measures for Baseline and Follow-up Assessments by Assessment Point	T0	T1	T2
Demographics; Financial Strain, , Household Smokers,	✓		
Tobacco Use History, Nicotine dependence, , Motivation to Quit	✓	✓	✓
Risk Perceptions: Child; Benefits of Quitting: Child	✓	✓	✓
Child's SHSe, , Child SHSe - related PED visits or Hospitalizations	✓	✓	✓
Healthy Habits Lifestyle- daily: fruits/vegetables, screen time, exercise, sugary drinks	✓	✓	✓
SBIRT and HHC Satisfaction,	✓		
Prolonged abstinence, point prevalence, nicotine dependence, readiness to change, quit attempts		✓	✓
Cessation Resource utilization: NRT, QL, SmokefreeTXT, Smokefree.gov, or other resources	✓	✓	

1. Demographics and tobacco use. We will collect gender, age, race/ethnicity, level of education, employment status, , number of cigarettes smoked daily, time to the first cigarette of the day, nicotine dependence, number of attempts to quit >24 hours, use of pharmacological and/or behavioral treatments for quitting, motivation to quit using the Contemplation Ladder, and stage of change in readiness to quit.^{41,72} Questions will also be asked about marijuana use by the participant and household members; participants will not be required to answer these questions. Participants who consented prior to Version 11 of the protocol may be re-consented at follow-up such that we may obtain information about marijuana use.

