2. Financial Strain. Three items will be used to measure financial strain.⁷⁴ The questions are: "How difficult is it for you to live on your total household income right now?", "In the next three months, how often do you think that you or your family will experience a bad time such as poor housing or not having enough food?", and "In the next three months, how often do you expect that you will have to do without the basic things that your family needs?" The three items will be measured on five-point scales and averaged to create a financial strain score ($\alpha = .802$). Higher scores will reflect more financial strain.

3. Risk perception to child. Perceived vulnerability regarding the effects of his/her smoking on their child will be assessed using adapted measures by Borelli et al. Perceived Vulnerability-Child will be measured with items including: "How concerned are you that smoking will make your child's illness worse?". Higher scores indicate higher perceived vulnerability.⁷⁷⁻⁷⁹

6. Benefits of quitting. We will assess whether the caregiver perceives that quitting smoking would have a beneficial effect on their child using the adapted precaution-effectiveness measures by Borelli, et. al. Precaution Effectiveness-Child (PE-C) will be measured by items including: "If you stop smoking, how much would that decrease your child's symptoms?". Higher scores indicate higher perceived vulnerability.⁷⁷⁻⁷⁹

7. Child's SHSe. Child's SHSe will be assessed by asking about family and other individuals with whom the child came in contact during the past week who smoke, locations of smoking, and number of cigarettes smoked. We will use questions adapted from previous studies.^{52,80-83} Caregivers who report no smoking indoors, outdoors, or in a car will be considered to have a complete smoking ban. Epic chart review will be conducted to assess SHSe-related PED visits and hospitalizations to CCHMC for 6-months prior to baseline.

8. Healthy Lifestyle Habits. We will assess healthy lifestyle practices (daily fruit/vegetable/sugary drink consumption, daily exercise and screen time) of all children.

9. Consumer satisfaction measure. SBIRT and HHC caregivers will complete a satisfaction survey measuring intervention satisfaction and perceived usefulness.⁸⁴

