11. Clinical and cost data. We will be evaluating the clinical characteristics and associated costs/charges of the baseline visit and hospitalization (if the child is hospitalized) and any SHSe-related or other visits or hospitalizations for the period up to 12 months prior and/or 12 months after the baseline visit. We will extract clinical data and costs from the charts that may include data on the presenting illness and illness severity (e.g., heart rate, respiratory rate, oxygen saturation, physical exam findings, triage level, chief complaint, discharge diagnosis, disposition), lab tests, procedures, interventions, and test results (if any), during these visits and/or hospitalizations.

12.

Follow-up Assessments (Table 1). All participants will be assessed at 6-weeks (T1) during home visits and at 6-months (T2) via phone or email; home visits will be made to conduct biochemical validation of caregivers and children when caregivers report that they have quit at T2. We will use self-report measures of prolonged abstinence and biochemically validated point prevalence at T1 and T2 to assess cessation.⁸⁵⁻⁸⁷ Point prevalence of tobacco use will be measured by the question: “Have you smoked, even a puff, in the last 7 days?” Caregivers will be considered abstainers if they report no tobacco use in the past 7 days. Prolonged abstinence will be measured by the question: “When did you last smoke a cigarette?” Response categories will range from “less than 1 month ago” to “more than 6 months ago.” Secondary outcomes will be assessed, including nicotine dependence, readiness to change, a quit attempt of \geq 24 hours, patterns of smoking, number of cigarettes smoked/day, treatment initiation, NRT or other pharmacotherapies used, QL, text, or web follow-up. As described above, we will use measures of child SHSe to assess children’s exposure and if home/car smoking bans are present. Secondary outcomes pertaining to the child’s SHSe, total home/car smoking bans, and SHSe-related healthcare utilization (PED visits or hospitalizations at CCHMC) will be assessed.

Biochemical Validation. At 6-weeks, we will conduct home visits to: (1) verify abstinence on caregivers who report that they have not smoked in the past 7 days via expired carbon monoxide testing and salivary cotinine (2) obtain

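### The only written rule for a smoking ban counts outdoor smoking against it, while the Aim 2 outcome is a home/car ban, and the plan does not reconcile the two

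*Combined protocol and SAP*

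**What the plan says.** The outcome is named consistently in the main places.

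- Purpose, Primary Aim 2: "Outcomes are caregiver reports of total home/car smoking bans and reductions in SHSe (validated using salivary cotinine in children".
- The matching hypothesis, in the same section, predicts a benefit on the same two locations: "Children of SBIRT caregivers will have higher total home/car smoking bans and lower home/car smoking exposure".
- Outcome Measures: "Child outcomes will be presence or absence of total home/car smoking bans, reported SHSe".
- The Aim 2 analysis text also speaks of home/car bans.

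The only sentence that says how a family is classified is in Baseline Assessment, item 7 (Child's SHSe): "Caregivers who report no smoking indoors, outdoors, or in a car will be considered to have a complete smoking ban". The same item says what is asked, namely about people "with whom the child came in contact during the past week who smoke, locations of smoking" and the number of cigarettes.

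Table 1 schedules the child SHSe measure at baseline, 6 weeks and 6 months. The Follow-up Assessments text then says "As described above, we will use measures of child SHSe to assess" the children's "exposure and if home/car smoking bans are present". It also places bans in a sentence on secondary outcomes: "total home/car smoking bans, and SHSe-related healthcare utilization (PED visits or hospitalizations at CCHMC) will be assessed".

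The validation text uses further labels. The 6-month text and the Biochemical Validation section refer to total home smoking bans. The 6-week text under Assessments and in the HHC protocol refers to total smoking bans with no location. No section says whether these labels and the complete ban of item 7 mean the same thing.

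**The concern.** The rule contains a location, outdoors, that the outcome does not. The intervention treats outdoor smoking as compatible with a home/car ban. Under SBIRT Protocol, Advise, caregivers who do not want to quit are given goals that shift cigarettes outdoors until none are smoked indoors or in the car. The sample fidelity checklist pairs a home/car ban with asking visitors to smoke outside. A family that follows this advice exactly could be scored as a failure on the ban outcome.

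At stake are the ban comparison in Aim 2 and, if the same variable is used there, the comparison of child cotinine by ban status. If item 7 is not meant to score the outcome, the home/car ban has a name but no written derivation, and the analyst must choose one later.

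**Working it through.** **Step 1. Apply both definitions to the same families.**

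| Smoking reported | Home/car outcome | Item 7 rule |
|---|---|---|
| None in home, car or outdoors | Ban | Ban |
| None in home or car; outdoors near the child | Ban | No ban |
| None in home or car; outdoors only, away from the child | Ban | Depends on what outdoors covers |
| Some in home or car | No ban | No ban |

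The definitions part in rows 2 and possibly 3, and always in one direction: home/car-ban families lose the ban. Item 7 asks about smokers the child met in the past week, so outdoors may mean only near the child. That reading removes row 3 but leaves row 2.

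**Step 2. Does the rule reach the outcome?** Item 7 sits under Baseline Assessment, but Table 1 repeats the measure at both follow-ups. The Follow-up Assessments text refers back to it for deciding on home/car bans. No other rule is written.

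**Step 3. Check the plan's power figure for bans.** Inputs from Sample Size and Power Estimates: 300 per group after 20% loss, HHC ban rate 50-65%, stated detectable difference 12 points at 80% power; with 375 per group, 11 points. No alpha is given for this calculation, so two-sided 0.05 is assumed. With d = p2 − p1 and p̄ the mean of p1 and p2:

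power = Φ{[d − 1.96·√(2p̄(1−p̄)/n)] / √[(p1(1−p1) + p2(1−p2))/n]}

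- HHC 50%, SBIRT 62%, n = 300: (0.120 − 1.96 × 0.0405)/0.0402 = 1.01, power 0.843.
- HHC 65%, SBIRT 77%, n = 300: (0.120 − 1.96 × 0.0371)/0.0367 = 1.29, power 0.902.
- HHC 50% to 65%, 11 points, n = 375: power 0.859 to 0.912.

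The difference detectable with exactly 80% power is 11.3 points (HHC 50%) to 10.4 points (HHC 65%) with 300 per group, and 10.2 to 9.4 points with 375. The stated 12 and 11 points are not reproduced exactly, but they err on the safe side.

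**Step 4. What would the item 7 rule do to the difference?** Let p_H and p_S be the true home/car ban rates in HHC and SBIRT, and s_H and s_S the shares of those families reporting no outdoor smoking. The observed difference is p_S·s_S − p_H·s_H. The amount lost from the true difference is p_S(1 − s_S) − p_H(1 − s_H). If s is equal in both arms, the difference shrinks by the factor s. If s differs, the loss can be larger, smaller or negative. The documents give a range for p_H but nothing for s_H or s_S, so the calculation stops here.

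**The case against.** The strongest reply is that item 7 defines a differently named variable. The label complete smoking ban appears nowhere else, and no section says that it is the Aim 2 outcome. The Follow-up Assessments text carries forward the measures, which include locations of smoking, and not that label. It can fairly be read as scoring home and car from the location items. The outcome's name states its locations, the SBIRT goal of ending indoor and car smoking matches it, and the Aim 2 analysis already names home/car bans for the cotinine comparison. The questionnaires (Appendices A, G and H) are listed by title only and may contain a direct home/car question.

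All of this stands as grounds for caution. The documents show two unreconciled definitions; they do not show that misclassification will occur. The reply supplies a likely intention, however, and not a written rule.

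Two stronger readings are tempting. A reader might infer that the rule biases the effect towards zero, because SBIRT moves smoking outdoors. This does not follow: SBIRT also aims at quitting, which would reduce outdoor smoking, and the documents give no outdoor-smoking share for either arm. A reader might also infer that a ban under item 7 collapses to abstinence, so that the expected HHC abstinence of 6.3% contradicts the 50-65% ban rate used for power. That holds only if the caregiver's own smoking anywhere outdoors counts. If outdoors means near the child, the documents give no rate to test.

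**Conclusion.** The concern holds as a conflict between the only written ban rule and the outcome it would have to score. It is conditional on the item 7 rule being used for the Aim 2 outcome. If so, families with a home/car ban who report outdoor smoking, at least near the child, are recorded as having no ban. If not, the derivation is unwritten.

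The size and direction of any effect on the group comparison cannot be derived from the documents. The 12- and 11-point power statements stand under a home/car definition (84-91% power, alpha assumed).

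Severity is minor to moderate. Aim 2 is titled primary, but the Follow-up Assessments text lists bans among secondary outcomes. The abstinence outcomes, reported SHSe and child cotinine as outcomes do not depend on the rule.

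**What to change.** Define the Aim 2 ban as no smoking by anyone inside the home and none in the car. Derive it from the smoking-location items at baseline, 6 weeks and 6 months. Use that one definition and one term in the aims, Outcome Measures, the Aim 2 analysis and the cotinine validation.

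Keep outdoor smoking near the child as a separate exposure item. If the complete smoking ban of item 7 is retained, label it a separate supportive variable and state whose outdoor smoking counts, and where.

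The cost is a short change of wording. Item 7 already asks about locations, so new data are probably not needed. Appendices A, G and H must be checked to confirm that home, car and outdoors are asked separately. The power statement for bans needs no change beyond stating its alpha.
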